4. CHANGES IN THE PLANNED ANALYSIS OF THE STUDY

4.1 ADDITIONS / NEW ANALYSES

In addition to the evaluations depicted in the CTP, the following evaluations will be added:

- Sensitivity Analyses for the primary endpoint
 - A tipping point analysis for the primary endpoint in both co-primary populations will be implemented. Details can be found in [Section 9.12.1](#).

4.2 CHANGES

The following changes compared to the plans outlined in the CTP will be implemented:

- In Section 7.3.2 (Secondary endpoint analyses) of the CTP it is written that convergence issues observed in the analysis of continuous endpoints via a restricted maximum likelihood (REML) based repeated measures approach would be tackled by applying different covariance structures. The exact wording is: "If this analysis fails to converge, the following covariance structures will be tested in order: heterogeneous toeplitz (TOEPH), toeplitz (TOEP) and autoregressive 1 (AR[1]). The first model to converge will be used." It is not intuitive why a different approach should be used for a secondary or further endpoint compared to what is done when the primary analysis shows similar issues. Hence, the analysis approach for convergence issues for continuous secondary or further endpoints will be modified to follow the one used for the primary analysis.
- In Section 7.3.2 (Secondary endpoint analyses) of the CTP it is written that Time-to-event (TTE) endpoints will be analysed using a Cox proportional hazards model. The exact wording is: "Time-to-event endpoints will be analysed using a Cox proportional hazards model. The equality of the hazard rates will be tested by the Wald test for the treatment effect at the two-sided 5% significance level. The model will include the treatment effect and HRCT pattern (except for the analyses on the co-primary analysis population assessing only patients with HRCT with UIP-like fibrotic pattern only) as covariates. Breslow's method for handling ties will be used. Kaplan-Meier plots by treatment group will also be presented. If the proportion of patients experiencing at least 1 acute ILD exacerbation over 52 weeks is less than 2%, then only frequencies of exacerbations by treatment group will be provided for the main secondary endpoint of time to first acute ILD exacerbation or death over 52 weeks and no statistical analysis will be performed." While the Cox Model is still employed to compute the effect size, i.e. the hazard ratio, a stratified log-rank test will be used to evaluate the effect of nintedanib on TTE endpoints compared to placebo.

4.3 CLARIFICATIONS

The following points warrant further clarification:

- Within this document, "drug intake" refers to the intake of the trial medication – either placebo or nintedanib.

- This study comprises of the following “populations”: The “overall” population and the subpopulation of patients with “HRCT with UIP-like fibrotic pattern only” are considered to be co-primary populations. The subpopulation of patients with “other HRCT fibrotic patterns” is considered to be the complementary population. Unless stated otherwise in the TSAP, evaluations are only done for the co-primary populations.
- In order to determine whether the results for the primary endpoint are consistent between the subpopulation of patients with “HRCT with UIP-like fibrotic pattern only” and the subpopulation of patients with “other HRCT fibrotic patterns” the following steps will be taken
 - The numerical results, including the 95% CI will be inspected visually
 - HRCT pattern will be treated as a subgroup in one sensitivity analysis, and the obtained interaction p-value will be depicted on a forest plot in addition to the results of the “overall” population, the subpopulation of patients with “HRCT with UIP-like fibrotic pattern only” and the subpopulation of patients with “other HRCT fibrotic patterns”. See [Section 7.4.3](#) for additional details.
- Due to the possible occurrence of mis-stratifications during the randomisation process, the HRCT pattern as reported in the eCRF will be used in all analyses. In case this occurs in more than 3% of all randomised patients, an additional sensitivity analysis is implemented utilising the values used during the randomisation process in the Interactive Response Technology (IRT) system. See [Section 7.4.2.2.2](#) for additional details.
- Two patients were randomised by mistake, whose disease extent was $\leq 10\%$ and whose HRCT pattern was not determined by the central readers. Both patients were randomised under “other HRCT fibrotic patterns”. Given that the HRCT pattern was actually not determined, those patients do not have an entry for this variable in the eCRF. They will be counted in the subpopulation of patients with “other HRCT fibrotic patterns” in all analyses within the CTR except for the sensitivity analysis implemented to evaluate the mis-stratifications – there they will be counted in the subpopulation of patients with “HRCT with UIP-like fibrotic pattern only”. See [Section 6.6](#) for further details.
- This study is only powered and adequately sized to evaluate the efficacy of nintedanib as determined by the primary endpoint analysis. To avoid confusion and misinterpretation, the depiction of p-values in the outputs will be limited to the following evaluations:
 - Primary analysis performed in the “overall population” and the co-primary population of patients with “HRCT with UIP-like fibrotic pattern only”
 - Sensitivity analyses of the primary endpoint analysis in both co-primary populations
 - Nominal p-values for the evaluation of the main secondary endpoints, evaluated in both co-primary populations

- Interaction p-values for the efficacy evaluations in the subgroup analyses (see [Section 6.4](#) for information about the devised subgroups)
- In Section 5.1.3 of the CTP, the following statement was made: “More details will be provided and additional further endpoints may be defined in the trial statistical analysis plan (TSAP)”
 - Details about further endpoints over the whole trial can be found in [Section 5.3.2](#).
 - No additional endpoints apart from those already mentioned in the CTP were defined for this trial.
- Due to the layout of this document, it may not be as straight forward to determine the different endpoints. To help with this and show the order of endpoints for CTR creation, below is an overview of the endpoints as depicted in Sections 5.1.1, 5.1.2 and 5.1.3 of the CTP:
 - Primary Endpoint
 - The primary efficacy endpoint is the annual rate of decline in FVC (expressed in mL over 52 weeks).
 - Secondary Endpoints
 - Main secondary efficacy endpoints
 - Absolute change from baseline in King's Brief Interstitial Lung Disease Questionnaire (K-BILD) total score at week 52
 - Time to first acute Interstitial Lung Disease (ILD) exacerbation or death over 52 weeks
 - Time to death over 52 weeks
 - Other secondary efficacy endpoints
 - Time to death due to respiratory cause over 52 weeks
 - Time to progression (defined as a $\geq 10\%$ absolute decline in FVC % predicted (pred)) or death over 52 weeks
 - Proportion of patients with a relative decline from baseline in FVC % pred of $>10\%$ at week 52
 - Proportion of patients with a relative decline from baseline in FVC % pred of $>5\%$ at week 52
 - Absolute change from baseline in Living with Pulmonary Fibrosis (L-PF) Symptoms dyspnea domain score at week 52
 - Absolute change from baseline in Living with Pulmonary Fibrosis (L-PF) Symptoms cough domain score at week 52

- Further Endpoints

- Further efficacy endpoints over 52 weeks (Part A)
 - Time to first non-elective hospitalization or death over 52 weeks
 - Absolute change from baseline in FVC (mL) at week 52
 - Absolute change from baseline in FVC % pred at week 52
 - Proportion of patients with an absolute decline from baseline in FVC % pred of >10% at week 52
 - Proportion of patients with an absolute decline from baseline in FVC % pred of >5% at week 52
 - Absolute change from baseline in DLCO % pred at week 52
 - Absolute change from baseline in Living with Pulmonary Fibrosis (L-PF) Total score at week 52
 - Absolute change from baseline in Living with Pulmonary Fibrosis (L-PF) Impact score at week 52
 - Absolute change from baseline in Living with Pulmonary Fibrosis (L-PF) Symptoms total score at week 52
 - Absolute change from baseline in Living with Pulmonary Fibrosis (L-PF) Symptoms Fatigue domain score at week 52
 - Absolute change from baseline in Pulmonary Fibrosis Impact on Quality of Life Scale (PF-IQOLS) summary score at week 52
- Further efficacy endpoints over the whole trial (Part A and Part B)
 - Time to first acute ILD exacerbation or death over the whole trial
 - Time to death over the whole trial
 - Time to death due to respiratory cause over the whole trial
 - Time to progression (defined as a $\geq 10\%$ absolute decline in FVC % pred) or death over the whole trial
 - Time to first non-elective hospitalization or death over the whole trial

5. ENDPOINTS

In this section, more details are given regarding endpoints. Note that for all endpoints and analyses, [Section 6.7](#) should be consulted for baseline value definition. For analyses that are specified over 52 weeks (Part A), unless otherwise specified, all data (including baseline) up to week 52 (inclusive – as defined in [Section 6.1](#)) will be taken into account, including follow-up visits before week 52 for patients who discontinue the trial medication prematurely. Analyses over the whole trial (Part A and Part B) reported at the time of the benefit-risk analysis will be based on all data collected until the data cut-off for DBL1. Analyses over the whole trial (Part A and Part B) reported after the final database lock (DBL2) will be based on all data collected within the trial.

Handling of missing data points is described in [Section 6.6](#).

For endpoints where the “date of last contact” is utilised, the following will apply:

- The last contact date when the patient was known to be alive is defined as the latest date recorded in the electronic Case Report Form (eCRF) from the dates listed below (in case a date is planned to be imputed for the analysis, the imputed date will also be used for the definition of “date of last contact”):
 - Date of last visit (e.g. for spirometry), data of last reported Adverse Event (AE) (excluding censored dates), date of last reported concomitant treatment, date of last laboratory sample, date of last drug intake, date of last reported dose change / interruption, last contact date (as documented on the termination of trial eCRF page if the reason for not completing the planned observation period is NOT “Death”), vital status date (from the vital status eCRF page if the patient is known to be alive) and the latest of vital status date / last successful contact date (from the vital status eCRF page if the patient was lost to follow-up).

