5.2.2.1.2 Time to death over 52 weeks

Date of death for an individual patient will be obtained from either the AE reporting page for patients with AEs leading to death or from the vital status assessment eCRF page.

For patients with known date of death (regardless of the cause of death) within the first 52 weeks the derivation will be as follows:

- Time to death [days] = Date of death – date of first drug intake + 1

Patients who did not experience any event within the first 52 weeks will be censored according to the mechanism for censoring as described in Table 5.2.2.1.2: 1 below.

Table 5.2.2.1.2: 1 Censoring Rules for Time to death over 52 weeks

Rule #	Situation	Outcome (event or censored)	Date of event or censoring
1	Patient died within the first 52 weeks and date of Death is known	Event	Date of event
2	Patient died within the first 52 weeks and date of Death is unknown	Event	Imputed date of event
3	Patient is alive after 52 weeks	Censored	Day 373 (372 days after first drug intake)
4	Patient status is unknown	Censored	Date of last contact when the patient was known to be alive

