6.6.2.2 Time-to-event endpoints

In the analyses of the time-to-event endpoints, missing or incomplete data will be managed by standard survival analysis techniques (i.e. censoring).

For the time to first acute ILD exacerbation, or first non-elective hospitalization in case of partially missing dates, the following imputation will be done:

- If day is missing, then imputed day will be the 15th of the month
- If day and month are missing, then imputed date will be the 1st of July of the (non-missing) year
- If year is missing, date will not be imputed

A missing or incomplete date of death will be imputed/completed so that the derived date is the earliest possible date which is on or after date of onset of the fatal AE, and on or after treatment start (in case this AE is treatment emergent), and on or after date of last contact.

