6.6.3 Other variables

6.6.3.1 Concomitant therapies

In case of (partially) missing start and end dates of concomitant therapies, the dates will be imputed so that the extent of exposure to the concomitant therapy is maximal, i.e. the first day (month) of the month (year) for incomplete start dates and the last day (month) of the month (year) for incomplete end dates.

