6.6.3.2 Safety endpoints

Missing or incomplete AE dates will be imputed according to BI standards ([7](#)).

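### The SAP's last-contact date can rest on an imputed date, or on a vital status date later than the last successful contact, so patients may be censored after they were last known alive

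*SAP*

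**What the plan says.** **Definition.** SAP section 5 sets the last contact to the latest eCRF date on a list covering visits, adverse events, laboratory samples, drug intake, dose changes, trial termination and vital status. The list also holds the "date of last reported concomitant treatment". Imputed dates count: "in case a date is planned to be imputed for the analysis, the imputed date will also be used for the definition of" the last-contact date. The vital status date of a patient known to be alive is one item. For a lost patient the item is "the latest of vital status date / last successful contact date (from the vital status eCRF page if the patient was lost to follow-up".

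**Imputation.** SAP 6.6.3.1 states the aim for concomitant therapies: "the dates will be imputed so that the extent of exposure to the concomitant therapy is maximal". Start dates go to the first day or month, and end dates to "the last day (month) of the month (year) for incomplete end dates". SAP 6.6.3.2 says "Missing or incomplete AE dates will be imputed according to BI standards", and that company standard is not reproduced. SAP 6.6.2.2 sets a missing or incomplete death date to the earliest date that meets several conditions, one of them "and on or after date of last contact".

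**Use.** In the 52-week table for time to death (SAP 5.2.2.1.2), Rule 4 censors a patient of unknown status at "Date of last contact when the patient was known to be alive". Rule 4 for the 52-week composites (SAP 5.2.2.1.3, 5.2.2.2.2, 5.3.1.1) adds that the patient must be event free. In the whole-trial tables (SAP 5.3.2.1 to 5.3.2.5), Rule 3 censors survivors by the last contact as well.

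**The concern.** A censoring date should be one up to which the patient was actually under observation. The definition claims this by speaking of a patient known to be alive, but then admits dates that nobody observed. A concomitant-therapy end date pushed to its latest possible day is a cautious choice for describing drug exposure. It says nothing about survival. For a lost patient, the rule allows a date after the last successful contact.

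At stake are the two time-to-event main secondary endpoints (time to death; time to first acute exacerbation or death), respiratory death, progression, hospitalisation and the whole-trial versions. Unobserved time would be counted as survival, which lowers the estimated event rate. Because last contact is also a floor for an imputed death date, a late last contact can delay a death too.

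**Working it through.** The plan states no figure for this point. Two nearby figures were reproduced first. With first intake as Day 1, 372 days later is Day 373, as in the censoring tables. From the pooled IPF mortality in protocol 1.2 (5.5% vs 7.8%), ln(1 − 0.055)/ln(1 − 0.078) = 0.697, matching the stated hazard ratio of 0.70.

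**1. How far the date can move**
- End date with day missing: up to 30 days.
- End date with day and month missing: up to 364 days, mean 182 if the true date is uniform over the year.
- Vital status date of a lost patient: the whole gap since last contact, up to about 372 days inside the 52-week window.

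**2. Example, censoring.** First dose 1 Feb 2018, last real contact 10 Mar 2018 (Day 38), and a drug end date recorded only as 2018. If the end date counts, it is imputed to 31 Dec 2018. Censoring falls on Day 38 + 296 = Day 334.

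**3. Example, death date.** First dose 15 Dec 2017, last seen 10 Dec 2018. The death and a drug end date are both recorded only as Dec 2018, with no later fatal-AE onset. From the real contact, death is imputed to Day 360 + 1 = 361, inside the window. With the drug end date imputed to 31 Dec, it becomes Day 381 + 1 = 382, past Day 373.

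**4. Effect on the 52-week death rate.** Assumptions: 300 per arm, constant hazards from the IPF mortality, a share *u* of unknown status with last real contact uniform over 0–372 days, and every such patient shifted (capped at the window). Formula: relative change in rate = PT/(PT + added time) − 1, where PT is true person-time.

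Hand check, ignoring deaths, *u* = 10%, shift to the end of the window: PT = 0.9 × 372 + 0.1 × 186 = 353.4 days per patient; added time = 0.1 × 186 = 18.6; 353.4/372 − 1 = −5.0%. The full calculation, with deaths:

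| Unknown status per arm | Shift 30 days | Shift 182 days | Shift 372 days |
|---|---|---|---|
| 1% | −0.1% | −0.4% | −0.5% |
| 5% | −0.4% | −1.9% | −2.5% |
| 10% | −0.8% | −3.8% | −5.0% (nintedanib), −5.1% (placebo) |

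**5. Effect on the hazard ratio (true value 0.697)**

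| Unknown status, nintedanib vs placebo | Shift 30 days | Shift 182 days | Shift 372 days |
|---|---|---|---|
| Equal (1%, 3%, 5% or 10%) | 0.697 | 0.697 | 0.697 |
| 10% vs 5% | 0.694 | 0.683 | 0.679 |
| 5% vs 1% | 0.694 | 0.686 | 0.682 |

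Hand check of 0.679: 0.697 × 0.950/0.975. With the arms exchanged, 0.697 × 0.975/0.950 = 0.715, so the direction depends on which arm loses more patients.

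**The case against.** The strongest reply has five parts.

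- **Start or end date.** The SAP does not say which concomitant-treatment date counts. Start dates are imputed to the earliest day, and SAP 7.2.2 classifies on-treatment therapies by start date. If the start date is meant, the first route disappears. This stands, so that route is conditional.
- **Vital status date.** A reader might infer that nobody reached a lost patient on that date. The documents do not support this as fact: the date is not defined for lost patients, and status may have been learned in another way. What stands is that the wording permits a date later than the last successful contact.
- **Deaths leaving the window.** SAP 6.6.2.2 picks the earliest admissible date, Rule 2 counts a death within 52 weeks on an unknown date as an event, and all deaths are adjudicated. Incomplete death dates should be few. The example above shows that a shift past Day 373 is possible, not that it is common.
- **Boundaries.** SAP 6.1.1 limits 52-week analyses to 372 days after first intake, and SAP section 5 limits the first whole-trial report to data collected by the cut-off. The first caps the gain at the window but does not prevent gain within it. The second restricts the data collected, not values imputed from them. The composites' event-free condition is a further limit, though the SAP defines no separate event-free date.
- **Frequency and weight.** Protocol 3.1 requires every attempt to obtain vital status at week 52, at the cut-off and at trial end. That should move most patients out of Rule 4 and give most survivors a real late date. P-values for these endpoints are nominal or not shown, and the trial is not powered for mortality. This limits the consequence but does not make the rule correct.

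**Conclusion.** The concern holds as a flaw in a stated derivation rule. SAP section 5 expressly admits imputed dates to a definition that claims knowledge of life, and for lost patients it permits a date after the last successful contact. The estimated death rate falls by about 0.1–5%. The hazard ratio is unchanged with balanced loss and moves by at most about 0.02 otherwise. These figures rest on assumed unknown-status shares of 1–10%, uniform last contact, IPF mortality and every unknown-status patient being shifted. The last assumption makes them upper figures for each share and shift. The whole-trial effect was not sized.

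Two stronger readings are not supported. A reader might infer that the rule favours nintedanib, but nothing in the documents shows which arm would lose more patients. A reader might also infer large inflation of follow-up as the usual result. A gain of 300 days needs a last real contact by about Day 73 (373 − 300), and nothing suggests that this is typical.

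**What to change.** In SAP section 5:
- Delete the clause that lets imputed dates count. Use only complete, recorded dates on which the patient was seen, reached or otherwise confirmed alive.
- For patients lost to follow-up, use the last successful contact date. Use the vital status date only if the patient was confirmed alive on it.
- Do not let the date exceed trial completion, the data cut-off or a recorded death date. An imputed death date must not serve as a cap, because it is itself derived from last contact.

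The death-date rule in SAP 6.6.2.2 then inherits the corrected date and needs no rewording. The cost is a few sentences and one derivation change, with no new data. The downside is that a few patients are censored earlier.

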5.1 PRIMARY ENDPOINT

The primary efficacy endpoint is the annual rate of decline in Forced Vital Capacity (FVC) over 52 weeks expressed in ml. The analysis will be based on FVC values obtained at pre-specified visits over 52 weeks (Part A). Handling of missing data points is described in [Section 6.6.1](#).

5.2 SECONDARY ENDPOINTS

5.2.1 Key secondary endpoints

This section is not applicable as no key secondary endpoint has been specified in the CTP.

5.2.2 Secondary endpoints

The secondary endpoints include change from baseline and time-to-event endpoints at or over 52 weeks. Please note: Additional information about the 52 weeks analysis period can be found in [Section 6.1.1](#), according to the type of endpoint.

5.2.2.1 Main secondary efficacy endpoints

5.2.2.1.1 Absolute change from baseline in King's Brief Interstitial Lung Disease Questionnaire (K-BILD) Total Score at 52 weeks

The K-BILD is a self-administered health status questionnaire that was developed and validated specifically for patients with ILD (12). The questionnaire consists of 15 items and 3 domains: breathlessness and activities, psychological, and chest symptoms. Possible score ranges from 0-100, with a score of 100 representing the best health status.

The K-BILD evaluation will primarily focus on the absolute change from baseline in the total score at week 52. To score the K-BILD, the Likert response scale weightings for individual items are combined, if necessary for certain items, to ensure they detect progressive change in health status. Then the scores are transformed to a range of 0–100 by using logit values and a look-up table to yield interval-level scores, where higher scores indicate better health status. The specific instructions for deriving the K-BILD total score are provided in [Section 9.1](#).

Specific rules of handling of missing items are detailed in [Section 6.6.2.1.1](#).

